6.2.3 Enrollment, Baseline, and Randomization

Enrollment

Prior to performing any study-related activities under this protocol, including screening tests and assessments, written informed consent with the approved ICF must be obtained from the subject in accordance with local practice and regulations. Once the subject has provided informed consent and passed the screening process, then he/she will they be considered enrolled.

Baseline Assessments

The baseline assessments are to be obtained after screening and randomization, but before the subject is started on the study assigned statin. These include:

- AMNART for English-Speaking Subjects or WAT for Spanish-speaking subjects
- NPT #1
 - Hopkins Verbal Learning Test (HVLT)
 - Rey Complex Figure
 - Grooved Pegboard
 - Trails A & B
 - Controlled Oral Word Association
 - Animal Naming
- CAM
- Blood Draw #1
 - Comprehensive Metabolic Panel (includes LFTs)
 - CK
 - Lipid Profile
 - CBC with differential
 - ESR (Sedimentation Rate)
 - C-Reactive Protein
- ApoE blood draw - Unlike other baseline assessments, the ApoE blood draw can be obtained at baseline or at any other time point during the subject's participation in the study.
- EKG from patient chart (e.g. part of pre-op testing)
- If applicable, Urine Pregnancy or Beta-HCGA (as part of pre-op testing)
- Demographics, Baseline Characteristics (handedness, education level, childbearing potential, tobacco/alcohol/substance use), medical history, and concomitant medications will be noted

Randomization

After subjects have passed the screening assessments, which should not take more than 15 minutes, the coordinator or other study personnel will either assign them to the Observational Arm (ARM 1) or randomize them within the arm corresponding to their current statin dosage status (ARM 2 and ARM 3). The randomization design will be stratified by center, previous use of statin and in random blocks of 4 and 6. The randomization process will be supported by the Statistical Analysis Center (SAC) at the Mailman School of Public Health at Columbia University. SAC will provide a central secure web-based randomization data system. All trials supported by the SAC employ central randomization that takes place in real-time. In other words, the patient's treatment assignment is made at the moment of randomization, based on probabilities calculated according to the randomization scheme, and communicated to the recruiting site via a central source (i.e. a secure web site).

Upon subject enrollment on the study website, the study drug start date will be noted for Arms 2 and 3. Those in the Observational/Maximal Dose group (Arm 1) will use a start date of the date of enrollment.

After randomization, the subject will complete the baseline assessments, the study drug will be requested and obtained from the site's research pharmacy and given to the subjects for self-administration on a daily basis as per protocol verbal and written instructions provided to each participant.

6.2.4 Neuropsychometric Evaluations

There will be four neuropsychometric battery of tests performed during the subject's participation in the study. Preoperative neuropsychometric tests will be used to evaluate patients pre- and post-operatively. The neuropsychometric tests are designed to demonstrate general neuropsychological performance and not to be diagnostic of specific neuropsychiatric disorders. The average amount of time to complete the neuropsychometric battery is around 45-60 minutes. There are three types of tests administered: (1) a general evaluation of mental status, (2) an evaluation of speed of mental processing, and (3) an evaluation of ability to learn using a list of words. They will be performed at enrollment, before surgery, one day after surgery (12-25 hours post-op for eCD) and at Day 30 +/- 5 days post CEA or day of their post-op clinical visit (dCD). eCD and dCD will be measured as significant change in neuropsychometric performance. Neuropsychometric performance will be determined by calculating Z-scores. In order to account for "practice effect" we will utilize a reference group of age matched patients having "simple spine" surgery. This group should be an effective reference group for the effect of anxiety, the trauma of surgery and the effect of medications on neuropsychometric performance. "Practice effect" arises because patients when repeatedly tested improve performance simply due to the effect of repetition.

The differences between NPT #1 administered upon enrollment and the other battery of neuropsychometric tests will be to consider the effects of changing the statin regimen approximately 2 weeks prior to CEA for arms 2 and 3. We will also review overall test changes, in all arms, from enrollment to Day of CEA (NPT#2).

The major cognitive domains the study is testing are:

- **Memory**
 - Verbal memory: **Hopkins Verbal Learning Test (HVLТ)**: Total Recall, Delayed Recall, and Recognition. The HVLТ was developed for the brief assessment of verbal recall and recognition (58, 59). The test consists of three learning/free-recall trials followed by a yes/no recognition trial. Test stimuli are 12 words, four from each of three semantic categories. Subjects are asked to recall the words (Total Recall). The HVLТ has six equivalent forms and takes less than 10 minutes to administer. These features make the HVLТ particularly suited to time constrained repeated assessment (e.g., drug trials, tracking neurological recovery) HVLТ has been shown to be stable over time (60). Visual Memory: Rey Complex Figure-Immediate Recall (61). The subject is asked to draw from memory the complex figure copied in the visuospatial task described below. The same standardized scoring system is used as for the copy task.
- **Constructive** ○ Visuospatial: **Rey Complex Figure Copy**: The subject is asked to copy the figure with all its detail properly located. A standardized scoring system, as described in Lezak (62), is used to score both the presence of specific design features and the accuracy of their location as well as the recall task.
- **Motor**
 - **Grooved Pegboard**: The subject places 25 notched-pegs into mirror image holes. The score is the time in seconds needed to complete this task. This test was selected because it combines both motor speed and dexterity with sensorimotor demands, making it sensitive to brain dysfunction. Because it is performed with both hands it can provide information about lateralization of brain dysfunction. This test was selected because it combines both motor speed and dexterity with sensorimotor demands, making it sensitive to brain dysfunction (56).
- **Executive** ○ **Trail Making Test, Part A** (63): The subject is asked to connect 25 numbered circles in ascending order with a single continuous line. The score is the time in seconds needed to perform this task. This speed-based task is a sensitive but relatively nonspecific indicator of brain dysfunction.
 - **Trail Making Test, Part B**: This test is similar to Trail Making Part A except that the 25 circles are numbered and lettered and the subject is asked to connect with a single line circles alternating between numbered and lettered sequences. The score is the time in seconds needed to perform this task. In addition to being a sensitive screening task, the alternation of letter and number sequences required by this task taps executive functions.
- **Language**
 - **Controlled Oral Word Association** (64a): The Controlled Word Association test will be administered. The patient is given 1 min to name as many words beginning with a particular letter as he/she can. This test is considered to be sensitive to frontal lobe damage.
 - **Animal Naming Test** to assess the verbal fluency of the individual and has been validated for testing MCI patients (64b).

In addition, we will also be testing for:

- **Pre-morbid Intelligence (pIQ) at Baseline Only** ○ As enhanced cognitive reserve may be a function of pre-morbid intelligence, we will administer the AMNART to all study and control patients who are English-speaking. If they are Spanish-speaking, please administer the WAT.

Either measure should take 5 additional minutes.

- **Post-operative Delirium** ○ The Confusion Assessment Method (CAM) will be used to screen for post-operative delirium in CEA patients and surgical controls at one day post CEA (12-25 hours post-op) and Day 30 +/- 5 days post CEA or day of their post-CEA clinical visit (48). See Section 2.1.5.

The main neuropsychometric battery of tests (NPT#1 – NPT #4) will consist of:

- Hopkins Verbal Learning Test (HVLT)
- Rey Complex Figure
- Grooved Pegboard
- Trails A & B
- Controlled Oral Word Association
- Animal Naming

6.2.5 Follow-up Visits [based on study drug start date (Arms 2 & 3) or date of enrollment (Arm 1)]

Call Day 3 (+/- 1 day) if CEA does not occur before day 3: •

Safety Compliance Questionnaire (telephone)

- TICS-M
- BLESSED ADL
- Medical Status/Concomitant Medications (review & add/edit from baseline)
- Adverse Event Assessment

Call Day 7 and 10 (+/- 1 day), if CEA does not occur before day 7 and 10, respectively:

- Safety Compliance Questionnaire (telephone)
- Medical Status/Concomitant Medications (review & add/edit from prior visit)
- Adverse Event Assessment

Day of CEA: The subject can have their pre-CEA testing done the actual Day of CEA or up to 18 days after enrollment/start of their study drug. All of their post-CEA testing needs to be done the actual Day of CEA after the surgery has been completed:

- Safety Compliance Questionnaire (in person)
- Collection of Study Medication Compliance form
- Collect Study Drug bottle and complete PILL COUNT
- Vitals
- EKG from patient chart (only if this is clinically required as part of SOC)
- NPT #2 ○ Hopkins Verbal Learning Test (HVLT)

- Rey Complex Figure ○
Grooved Pegboard ○ Trails A
& B
- Controlled Oral Word
Association ○ Animal Naming
- CAM
- Blood Draw #2 ○ Comprehensive Metabolic Panel (includes LFTs) ○ CK
○ Lipid Profile ○ CBC with
differential ○ ESR
(Sedimentation Rate) ○ C-
Reactive Protein
- Collect ApoE blood draw (if not collected at baseline)
- Medical Status/Concomitant Medications (review & add/edit from prior visit)
- Neurological Exam (Day of CEA post-op from chart)
- Adverse Event Assessment

Day 1 Post CEA (12-25 hours post-op):

- Safety Compliance Questionnaire (in person)
- Vitals
- NPT #3 ○ Hopkins Verbal Learning Test (HVLT)
○ Rey Complex Figure ○
Grooved Pegboard ○ Trails A
& B
- Controlled Oral Word
Association ○ Animal Naming
- CAM
- Collect ApoE blood draw (if not collected at baseline)
- Medical Status/Concomitant Medications (review & add/edit from prior visit)
- Neurological Exam (post-op from chart)
- Adverse Event Assessment

Call Day 7, 14, & 21 Post CEA (+/- 3 day):

- Safety Compliance Questionnaire (telephone)
- Medical Status/Concomitant Medications (review & add/edit from prior visit)
- Adverse Event Assessment

Day 30 Post CEA (+/-5 days) or Day of PO Visit:

- Safety Compliance Questionnaire (in person)
- Vitals
- NPT #4 ○ Hopkins Verbal Learning Test (HVLT)

- Rey Complex Figure ○ Grooved Pegboard ○ Trails A & B
- Controlled Oral Word Association ○ Animal Naming
- CAM
- Blood Draw #3 ○ Comprehensive Metabolic Panel (includes LFTs) ○ CK ○ Lipid Profile ○ CBC with differential ○ ESR (Sedimentation Rate) ○ C-Reactive Protein
- Collect ApoE blood draw (if not collected at baseline)
- Medical Status/Concomitant Medications (review & add/edit from prior visit)
- Adverse Event Assessment

6.2.6 Completion/Final Evaluation

Call Day 365 (+/- 30 day):

- Safety Compliance Questionnaire (telephone)
- TICS-M
- BLESSED ADL
- Medical Status/Concomitant Medications (review & add/edit from prior visit)
- Adverse Event Assessment
- Upon completion of the study or at any time when subject discontinues his/her study participation, the coordinator will interview the participant to complete the study's Completion Form, Discontinuation Form or have reported their death as an SAE.

6.3 Local and Central Laboratory Procedures

The participants' three blood draws for Comprehensive Metabolic Panel (CMP), Creatine Kinase (CK), Lipid Profile, CBC with differential, Sedimentation Rate (ESR), C-Reactive Protein (CRP), and their corresponding laboratory tests will be analyzed at each site's institutional laboratory and the results will be recorded in the participant's medical record (source document).

The ApoE blood draw is different as it will only be taken once during the subject's study participation and will be analyzed centrally. Unlike other baseline assessments, this blood draw can be obtained at baseline or at any other timepoint during the subject's participation in the study.

The ApoE blood draw will be shipped to the Central Coordinating Center (CCC) at:

IGM Biobanking Core, CUMC
[name] New
York, NY 10032
Attn: [name].
[contact]

IGM Biobanking will be in charge of receiving ApoE blood samples, extracting the DNA and storing the biological specimens until they are ready to be tested for ApoE. IGM will use the Isolation of (high molecular weight) HMW genomic DNA from blood by using the salting out purification protocol which is a standard DNA isolation method.

The extracted DNA samples will be plated by IGM and sent to LGC Genomics for ApoE allele testing at:

LGC Genomics
Att: [name]
[name]
[name]
[name]
[contact] www.lgcgroup.com

LGC uses KASP genotyping chemistry on their own instrumentation to genotype samples. Briefly, they first perform a quality check on the customer DNA by using a serial dilution of the DNA and genotyping on internal quality control assays. Once passing QC, PCR plates in either 384 well or 1536 well format are prepared using an automated liquid handler (RepliKator) at the appropriate dilution from the testing and dried in an oven. They then apply the primer and PCR master mix on the dried down DNA using a semiautomated dispenser engine (Meridian). Once the reagents are added, the plates are sealed via a laser sealer (Fusion). PCR is performed using an automated water bath machine (Hydrocycler) using a touchdown procedure with denaturation temperature of 94 and annealing temperatures from 61 to 55 for the first 10 cycles and then 55 for an additional 26 cycles (there is no extension step). Fluorescence is measured using a plate reader (PheraStar, BMG Labtech). As they read the plates toward the end, but still within the exponential phase of PCR, they perform an additional 3 cycles of PCR and re-read the plates until clustering of the samples is complete. The clustering data is checked by experienced staff members and then second checked by a senior member of staff before being exported and results sent out. For the ApoE testing, they use two SNPs, rs429358 and rs7412.

7 SAFETY ASSESSMENTS

7.1 Clinical Risks

Patients will have clinical laboratory tests upon enrollment and a research coordinator or nurse will contact them 3 days after starting the study drug to verify the patient's complying with the statin regimen as well as to ask questions regarding their subjective experience of taking the study assigned statin regimen (if the CEA does not occur prior to day 3). If the CEA does happen prior to day 3, the Day of CEA Safety Questionnaire will verify compliance and ask about the subjects experience with the assigned statin regimen. Patients will be asked about a variety of symptoms associated, though rarely, with statin use. According to the FDA, the value of statins has been clearly established yet they also advise that statins,

including the ones which will be part of this study (i.e. simvastatin, atorvastatin and rosuvastatin) offer some rare, but potential risks to statin users:¹

- Hepatic toxicity (indicator symptoms: elevated liver enzymes, bleeding or jaundice)
- Muscle toxicity (indicators symptoms: myalgia and arthralgia)
- Increased glucose levels

In addition, from clinical practice, we also know that statins may produce some minor gastrointestinal discomfort; however, these are minor and mostly tolerated as the benefit of statins tends to outweigh the minor stomach upsets they may produce in some individuals.

Patients randomized to maximize their statin regimen or randomized into the atorvastatin 80mg group are the only patients we anticipate having any risk of side effects.

If a patient reports subjective experiences of side effects, their statin regimen will be modified at the discretion of the caring physician. Although the randomization of the patient is compromised, we will continue to evaluate that patient and proceed with intention to treat principles. If the laboratory values the morning of surgery present with elevations in CK or LFT, their statin regimen will be modified at the discretion of the caring physician.

Other Potential Study Procedure Risks:

- Some people may feel uncomfortable taking cognitive tests.
- Slight pain and/or temporary discoloration of the skin after blood draws.
- Unlikely, but potential breach of confidentiality

7.2 Specification of Safety Parameters

7.2.1 Protection Against Clinical Risks

Protection against other statin drugs being given to the subject participants prior to CEA:

- A letter for the subject's Primary Medical Doctor will be prepared to avoid duplication of prescribed statin doses or unknown changes to their statin regimen (see Appendix VI).
- Although extremely rare in FDA approved statin doses, the risks associated with statin use such as myalgias, arthralgias, gastrointestinal distress, or elevation in blood sugar can occur in some individuals.² Consequently, consented participants will first have various laboratory tests and assessed for clinical symptoms to assure safety. The laboratory tests conducted at baseline, Day of CEA, Day 1 post CEA (12-25 hours post-op) and 30 +/- 5 days post CEA or Day of post-op clinical visit. These include: CBC w/differential, comprehensive metabolic panel (which includes blood glucose levels, creatinine, and Hepatic LFTs), CK, and a lipid profile to detect any physiologic symptoms associated with the statin intervention.

¹ (<http://www.fda.gov/ForConsumers/ConsumerUpdates/ucm293330.htm>):

² (<http://www.fda.gov/ForConsumers/ConsumerUpdates/ucm293330.htm>):

- Abnormal lab results at baseline: anyone with elevated CK (5x > ULN) or LFTs (2x > ULN) will not be asked to take the study drug. These subjects will screen out from the study, and their future statin regimen will be determined by their treating physician. The blood draw will not be done fasting; however, anyone with abnormally high and uncontrollable blood glucose levels will also be screened out. All of the results will be reported to the subject participants via phone and advised to address abnormal results will become part of their medical record.
- Abnormal lab results on Day of CEA, Day 1 post CEA (12-25 hours post-op) and/or Day 30 +/- 5 days post CEA (or Day of PO clinical visit): anyone with elevated CK and LFTs will be considered an AE. Anyone with CK 5x > ULN with symptoms or 10x > ULN without symptoms and/or LFTs 2x > ULN with symptoms or 3x > ULN without symptoms will be considered a Serious Adverse Event. Also, their statin regimen will be determined by their treating physician who will be made aware of the abnormal findings. The results will also be in the patient's medical records and available for the treating physicians to address. We will continue to follow them for the remainder of the study to assess for safety.
- We will report any abnormal laboratory values **not present at baseline** as adverse events. This will include abnormal laboratory values showing any potential acute kidney injury (AKI) defined as a serum creatinine increase of 50% from baseline within 7 days.³
- Clinical study assessments for statin intolerance will be done via phone using structured questionnaires to assess for safety/adverse events and compliance on:
 - Day 3 (+/-1d) if not preceded by CEA, 7 (+/- 1d) if not preceded by CEA, 10 (+/- 1d) if not preceded by CEA and Post-CEA: Day 7 (+/- 3d), Day14 (+/- 3d), Day 21 (+/- 3d), and Day 365 (+/- 30d)
- Clinical assessments for statin intolerance will be done in person while the patient is in the hospital for their CEA and during Day 30 +/- 5 days post-CEA or in-person the day of their post-CEA clinical visit.
- In addition, while the patient is in the hospital for the CEA, we will monitor the medical chart for any adverse events (clinical or laboratory based).

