7.2.2 Protection Against Other Minor Procedure/Study Related Risks

- It is expected that some individuals may feel uncomfortable taking cognitive tests; consequently, we will make every effort to ensure subject participant comfort during their neurocognitive testing.
- There will be three blood draws which could potentially produce minimal pain, bruising or discomfort; however, blood draws will be conducted by trained professionals which will minimize any of the above mentioned risks
- Every effort will also be made to ensure the confidentiality of the subject participant, including the use of unique patient identifiers for the study forms, and database entry. The subject binders/data

³ http://www.kdigo.org/clinical_practice_guidelines/pdf/KDIGO%20AKI%20Guideline.pdf

will be kept in a locked cabinet within a locked room which is only accessible to the study team. If any subject contact information is kept digitally, it will be kept in a password protected computer only accessible to authorized study personnel.

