7.5 Reporting Procedures

All AEs will be reported by the local Principal Investigator or designee using the study NSAE/SAE form and based on the Common Terminology Criteria for Adverse Events (CTCAE v.4.03)⁴ for language and severity

⁴ CTCAE_4.03_2010-06-14_QuickReference_8.5x11 <http://evs.nci.nih.gov/ftp1/CTCAE/About.html>

grade criteria. Data regarding timing, seriousness, severity, expectedness, resolution, study drug action taken, if AE resulted in withdrawal from the study, and relationship to the drug along with a preliminary narrative summary will be entered in the NSAE/SAE form. The supporting documentation will also be included with the NSAE/SAE form. All of the AE information will also be entered and uploaded into the study database. The timing of adverse event reporting will correspond to the type of adverse event as noted below (i.e. NSAE, SAE, Unexpected, SUSAR). All semi-annual DSMB/Progress reports will contain details of all NSAEs and SAEs, including any unexpected events or suspected unexpected serious adverse reactions (SUSARs).

In addition to the CTCAE criteria, to screen for acute kidney injury (AKI), we will use the definition provided by the Kidney Diseases Improving Global Outcomes (KDIGO) Clinical Practice Guideline for Acute Kidney Injury (vol 2, issue 1, March, 2012) which states that AKI can be defined by an increase from baseline in serum creatinine (SCr) by 50% within 7 days.³

The Independent Medical Monitor (IMM), [name], will indicate to the Sponsor, Statistical Analysis Center (SAC), and DSMB through [name]/NIA officer whether there are any concerns after review of semi-annual reports. In addition, if the IMM determines that there are any concerns between semi-annual reports or after reviewing SAE reports, the IMM will also notify the Sponsor, SAC, and DSMB, and DSMB ISO through [name]. A teleconference will be conducted with the IMM as needed.

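### The AKI screen counts 7 days from baseline, so at the planned lead of about two weeks a surgery-day creatinine cannot meet it

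*Combined protocol and SAP*

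**What the plan says.** The rule appears twice. Section 7.2.1 includes among reportable laboratory abnormalities those showing "potential acute kidney injury (AKI) defined as a serum creatinine increase of 50% from baseline within 7 days". Section 7.5 adds it to CTCAE grading as the screen for kidney injury, stating that "AKI can be defined by an increase from baseline in serum creatinine (SCr) by 50% within 7 days".

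Creatinine comes from the metabolic panel. Sections 6.1 and 6.2.5 and Appendix I place that panel at baseline, CEA day, and Day 30 ± 5 or the post-operative visit. Section 7.2.2 agrees on the number of samples: "There will be three blood draws which could potentially produce minimal pain, bruising or discomfort". Section 7.2.1 differs, with a fourth time point: "The laboratory tests conducted at baseline, Day of CEA, Day 1 post CEA (12-25 hours post-op) and 30 +/- 5 days post CEA". The Day 1 column of the schedule and the Day 1 visit list contain no such panel.

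On timing, section 5.1 allows 2 to 18 daily doses before CEA and asks sites to enrol early so that subjects get as many as possible. Section 6.2.4 describes "the effects of changing the statin regimen approximately 2 weeks prior to CEA for arms 2 and 3". The Day of CEA entry in section 6.2.5 gives some freedom: "The subject can have their pre-CEA testing done the actual Day of CEA or up to 18 days after enrollment/start of their study drug".

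**The concern.** The rule needs a second creatinine within 7 days of baseline, and the schedule does not fix one there. Whether a 50% rise is called AKI therefore depends partly on how soon surgery, or an early Draw #2, followed Draw #1. Two patients with the same rise can be classified differently only because their operations were booked at different distances. Patients with the longest leads, who take the most study drug, are the least likely to have a qualifying surgery-day value.

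Safety is part of the purpose stated in section 1.1, and section 7.5 names this definition as the screen. A low AKI count under the rule would say little about patients with longer leads.

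**Working it through.** The plan gives no figure to reproduce, so the check is calendar arithmetic.

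**Inputs**
- Window: 7 days from baseline (7.2.1, 7.5).
- Baseline: Draw #1. Section 6.2.3 lists it among the baseline assessments, taken before study drug starts. Section 7.2.1 names baseline and Day of CEA as separate laboratory time points.
- CEA day: D2 to D18 (6.1), which is 17 permitted days.
- Draw #3: 25 to 35 days after CEA when taken at Day 30 ± 5.
- Assumption: Draw #1 is on the day of Dose 1. This is the favourable case, because section 6.2.2 also uses Draw #1 for screening before randomisation, and an earlier Draw #1 only lengthens the interval.

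**Draw #2 on CEA day d**

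| Numbering | Interval from Draw #1 | Range | 7 days or less | More than 7 days |
|---|---|---|---|---|
| Dose 1 = Day 1 | d − 1 | 1 to 17 | D2–D8: 7 of 17 | 10 of 17 |
| Dose 1 = Day 0 | d | 2 to 18 | D2–D7: 6 of 17 | 11 of 17 |

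At a 14-day lead the draw is 14 − 7 = 7 days past the limit, or 14/7 = 2 times the window. At an 18-day lead it is 18 − 7 = 11 days past.

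**Draw #3 at Day 30 ± 5**
- Dose 1 = Day 1: 1 + 25 = 26 to 17 + 35 = 52 days after Draw #1.
- Dose 1 = Day 0: 2 + 25 = 27 to 18 + 35 = 53 days.
- Every value is outside the window. The alternative of a post-operative visit has no stated lower limit, although the Precis puts that visit at about 30 days.

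**Early Draw #2**
- The latest qualifying draw is 7 days after Draw #1. It follows 7 doses, or 8 if that day's dose is taken before the draw.
- For a 14-dose course this covers 7/14 = 50% to 8/14 = 57% of doses. For 18 doses it covers 7/18 = 39% to 8/18 = 44%. The remaining doses before surgery then have no scheduled creatinine.

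**Day 1 post-CEA labs, if drawn**
- At a 14-day lead they fall 14 + 1 = 15 days after baseline, also outside. They would be close to a CEA-day Draw #2, but the rule counts from baseline.

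**Deferred starters (5.1)**
- These subjects enrol more than 18 days before CEA, so with Draw #1 at enrolment a CEA-day Draw #2 is at least 19 days later.
- If dosing starts 18 days before CEA, a Draw #1 at 25 days is 25 − 18 = 7 days before Dose 1. At 26 days it is 8 days before, so the window closes before any study drug is taken.

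**What other reporting can miss**
- A patient whose Draw #1 creatinine is below 1/1.5 = two-thirds of the upper limit of normal can rise by 50% and stay below that limit. A rule that depends on an abnormal value need not pick this up.

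**The case against.** The strongest reply is that late rises are already covered. Section 7.2.1 reports any abnormal laboratory value not present at baseline. Section 7.4 counts clinically significant abnormal results that are new or worsened, with no 7-day limit and no causality judgement. Section 7.5 applies CTCAE, and sections 7.2.1 and 7.3 provide for review of the hospital chart. This stands. A reader might infer that kidney injury found at two weeks or later goes unreported; the documents do not support that.

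The 7-day limit also belongs to the definition that the protocol cites. A rise seen only across two weeks does not show onset within 7 days, so withholding the acute label is reasonable. This stands too, and it is why the label should be kept and not stretched.

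It can be argued that baseline means the morning of surgery, as section 9.1 has it. That usage concerns cognitive scores. For laboratory tests, sections 6.2.3 and 7.2.1 point to Draw #1. The alternative would also lean on Day 1 labs that the schedule does not contain.

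The freedom to take Draw #2 early is real, but nothing requires it to fall within 7 days.

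Finally, section 7.3 quotes a source finding no evidence that statins cause kidney damage, and section 4.2 excludes creatinine above 2.5 mg/dL. Both argue for low priority. Neither makes the chosen screen workable at the planned lead.

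**Conclusion.** The mismatch holds, as a minor safety-reporting correction. With baseline read as Draw #1, a CEA-day Draw #2 meets the rule on 6 or 7 of 17 permitted CEA days and not at a lead of about two weeks. A Draw #3 at Day 30 ± 5 never meets it.

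The 6 or 7 of 17 must not be read as a share of patients. The plan gives neither the distribution of leads nor the number of deferred starters, so the proportion affected is unknown.

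What is lost is the AKI label and possibly 50% rises that stay within the normal range. The documents do not show whether CTCAE grading would catch the latter. The cognitive outcomes and the randomised comparison are unaffected.

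**What to change.** In sections 7.2.1 and 7.5:

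1. Flag for safety review, and tabulate by arm, any creatinine at Draw #2 or Draw #3 that is at least 1.5 × Draw #1, with the interval in days. Pass flagged values to adverse-event reporting under the existing definition in section 7.4. The flag should not make every such rise an adverse event automatically.
2. Keep the 7-day AKI label for a 50% rise shown between two available values 7 days or less apart, including hospital chart values.
3. Report the two counts separately.
4. Use Draw #1 as the reference for the flag in all patients, including deferred starters, so that the reference is the same for everyone.

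The cost is wording in two sections and one derived flag from creatinine values already collected. No visit or blood draw is added. The downside is that some late, non-acute rises will be flagged; the recorded interval and the separate counts keep them distinguishable from AKI.
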